7.0 Expected Risks/Benefits

The risks to subjects involve risks of 1) confidentiality, 2) administration of methamphetamine, 3) completion of questionnaires, and 4) blood draws. The possible adverse effects of methamphetamine include:

- constipation
- memory loss
- dizziness or faintness
- restlessness
- double or blurred vision
- shakiness or tremor
- coordination problems
- changes in sex drive
- rapid heart rate
- dryness of the mouth
- raised blood pressure
- nausea or muscle weakness
- drowsiness
- depression
- confusion
- tiredness
- slurred speech
- headache

These reactions are unlikely at the dose administered in this study, and in these healthy volunteers. In addition, subjects must report prior recreational use of illicit drugs including amphetamines, without adverse effects. We have previously administered 20mg methamphetamine in our laboratory with few, if any, adverse effects. In order to minimize risks to subjects, we will only enroll individuals who report previous recreational drug use including alcohol, tobacco or marijuana use. The large majority of occasional psychoactive drug users do not go on to use them excessively and there is no evidence that participating in controlled laboratory studies such as these increases the risk for developing substance use problems [18-21].

Some risks are associated with the blood draw. These include bruising and pain at the site of needle insertion, and a small risk for infection. Samples will be drawn by a certified phlebotomist who is trained in methods of reducing risks. In addition, standard sterilization techniques will be utilized in order to minimize the risk of needle-site infections.

Potential benefits of the proposed research to subjects and others: subjects will benefit from the information obtained during the screening procedure (e.g., physical examination and electrocardiogram, as well as psychiatric screening). This is particularly beneficial to individuals who are excluded during the screening because of some previously undiagnosed condition. These individuals are referred for treatment. Subjects are paid for their participation. They may also request information about their performance and responses during the studies.

Importance of the knowledge to be gained: the risks to subjects are justified by the knowledge to be gained. The findings will further our understanding of an important yet understudied clinical issue in a controlled manner, that is, how psychoactive substances come to powerfully control mood and behavior which is central to the development of drug addiction. The project will be important to the wider addiction research community, both basic science and clinical. The findings will be important from a basic science and also a clinical perspective. This human model has a clear parallel in preclinical research and provides a critical translational link to preclinical data. An understanding of how contextual conditioning is established with the prototypical stimulant drug methamphetamine can be applied to the processes of contextual conditioning of other drugs. The findings and model can be used to design future investigations into methods to disrupt contextual conditioning and its consequences, particularly conditioned drug craving. Ultimately the data will inform existing treatment practices e.g. exposure therapy, and aid development of new approaches to curb drug use. Thus, new methods that break contextual associations or which counteract their influence on mood and behavior will improve current strategies to help achieve and maintain drug abstinence.

8.0 Data Collection and Management Procedures

Subjective data will be collected using standardized paper forms and computerized questionnaires. Each subject will be given a unique code. The data will only be identified with the subject's ID for that study. The PI will keep the codes that link the name of the participant

and the study ID in a secured cabinet. Data from paper forms will be entered in the computer by trained staff, and discrepancies corrected by a supervisor based on source documents. Computerized tasks will be administered using ACCESS and stored in a database on password protected computers in the PI's laboratory.

9.0 Data Analysis

The primary measures are (i) change in % time spent in the drug-paired room, (ii) ratings of subjective stimulation (ARCI) during conditioning, and (iii) ratings of subjective stimulation during the re-exposure test session. Sample size calculations are presented in table 1 (below).

Aim 1a: **To determine the influence of methamphetamine place conditioning upon time spent in the drug-paired context.** We hypothesize that the paired group will spend significantly more time in a context paired with methamphetamine at test than the unpaired group. We will compare the change in time spent in the initially less-preferred room between the paired and unpaired groups using t-tests.

Aim 1b: **To determine the relationship between individual differences in methamphetamine place conditioning and (i) acute responses to the drug, (ii) demographic characteristics.** We hypothesize that individuals who exhibit greater sensitivity to the acute positive subjective effects of methamphetamine will exhibit the largest increases in time spent in the drug-paired context at test. We will examine the association between methamphetamine subjective responses (stimulation and drug liking) after the first administration and the change in time spent in the drug-paired room at test using correlation analysis. Power calculations based on an N of 90, with 80% power and a significance level of $p<0.05$ (2-sided) indicate that we will be able to detect a significant association if the true correlation coefficient is 0.3 (a medium effect size). In exploratory analyses we will investigate differences in demographic, personality and drug use characteristics between paired group subjects who acquire conditioning ($\geq 10\%$ increase in time spent in drug-paired room) in comparison to those who do not (no change or a decrease in time spent in drug-paired room) using independent sample t-tests. Pilot data from our studies indicates that approximately 30% of subjects do not acquire conditioning.

Aim 2: **To determine context-dependent responses to methamphetamine and placebo challenge following place conditioning with methamphetamine.** We hypothesize that methamphetamine will produce greater subjective stimulation among subjects tested in the drug-paired room than those tested in the placebo-paired room. We will compare subjective stimulation after 20mg methamphetamine between paired group subjects tested in the drug-paired and placebo-paired rooms using independent samples t-test.

Table 2: Calculations of ¹required sample size to detect observed effects (2 sided test, $\alpha=0.05$, power=80%) and ²the probability to detect significant differences for the specific aims. Calculations were based upon preliminary data (section C1.4). *indicates a within-subjects t-

test. [#]indicates a between-subjects *t*-test. ^{*}Sample sizes are lower than the number enrolled in each group as we expect 70% of subjects in the paired groups to acquire conditioning (Fig 3b).

Aim	Outcome Measure	N[*]	SD	Difference	N¹	Power²
1a	Change in % time spent in drug-paired room*	60	22.7	12.4	30	98
	Change in % time spent in drug-paired room [#]	80	20.0	13.7	70	85
2	Stimulation ^a (ARCI A) [#]	40	11.0	13.0	26	95

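### Aim 1b tests one hypothesis with two correlations, each at 5%, and names neither a lead predictor nor an adjustment; if either counts, the false-positive rate is about 8 to 9.5%

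*Combined protocol and SAP*

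**What the plan says.** Section 9.0 (Data Analysis) gives each aim its own hypothesis and test.

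- **Aim 1a:** "We will compare the change in time spent in the initially less-preferred room between the paired and unpaired groups using t-tests".
- **Aim 1b:** one hypothesis, that "individuals who exhibit greater sensitivity to the acute positive subjective effects of methamphetamine will exhibit the largest increases in time spent". The test is a correlation analysis of change in room time against "methamphetamine subjective responses (stimulation and drug liking) after the first administration". The power statement uses N = 90, 80% power, a two-sided 0.05 and a true correlation of 0.3.
- **Aim 2:** "We will compare subjective stimulation after 20mg methamphetamine between paired group subjects tested in the drug-paired and placebo-paired rooms using independent samples t-test".

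The list of primary measures begins "The primary measures are (i) change in % time spent in the drug-paired room, (ii) ratings of subjective stimulation (ARCI) during conditioning" and ends with stimulation at the re-exposure session. Drug liking is not among them. Within Aim 1b only the comparison of subjects who do and do not acquire conditioning is called exploratory; the two correlations are not. Section 12.0 refers back to section 9.0. Neither section sets a multiplicity rule, an order of testing or an overall significance level.

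**The concern.** Stimulation and liking are both positive subjective effects, so a significant correlation with either could be reported as confirming the Aim 1b hypothesis. The plan attaches 5% to each correlation but does not say what the hypothesis as a whole requires. Two routes to one conclusion give a higher error rate than either route alone. What is at stake is the credibility of the individual-differences claim: a reader who sees one significant correlation out of two could not tell whether it was the one the investigators had committed to.

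**Working it through.** **Inputs from the documents.** Aim 1b: N = 90, r = 0.3, two-sided 0.05, 80% power (section 9.0). Paired groups: 3 × 40 = 120 subjects (section 4.0).

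**Assumption.** The correlation ρ between the two test statistics is not given. When neither predictor is related to room time, ρ is approximately the correlation between stimulation and liking themselves. The range shown is 0.3 to 0.7.

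**1. Reproduce the plan's figure.** By Fisher's z, atanh(0.3) = 0.3095.

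- Required N = ((1.960 + 0.842)/0.3095)² + 3 = 84.9, so 85.
- Power at N = 90 = Φ(0.3095 × √87 − 1.960) = Φ(2.887 − 1.960) = Φ(0.927) = 82.3%.

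The statement that N = 90 gives at least 80% power is correct for one correlation.

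**2. Error rate if either correlation counts.** With both nulls true, the rate is 1 − P(|Z₁| < 1.960 and |Z₂| < 1.960), with Z₁ and Z₂ bivariate normal.

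| ρ | Either significant |
|---|---|
| 0 | 9.75% |
| 0.3 | 9.5% |
| 0.5 | 9.1% |
| 0.7 | 8.3% |
| 0.9 | 7.0% |
| 1 | 5.0% |

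These count errors in either direction. In the hypothesised direction alone the rate is about half: 4.2% to 4.8% for ρ of 0.7 to 0.3, against 2.5% for one test.

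**3. Error rate if both must be significant.** P(both) = 0.05 + 0.05 − P(either), which is 0.5% at ρ = 0.3 and 1.7% at ρ = 0.7. The two readings of the same text therefore differ widely in error rate.

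**4. Power under Holm for the pair.** Holm rejects a given correlation if its |Z| exceeds 2.241 (two-sided 0.025). It also rejects if |Z| lies between 1.960 and 2.241 and the other correlation exceeds 2.241. Its power therefore lies between the power at 0.025 and the power at 0.05.

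| | N = 90 | N = 120 |
|---|---|---|
| Mean of Z at r = 0.3 | 2.887 | 3.348 |
| Unadjusted, 0.05 | Φ(0.927) = 82% | Φ(1.388) = 92% |
| At 0.025 | Φ(0.646) = 74% | Φ(1.107) = 87% |
| Holm, both associations real (simulated, ρ = 0.5) | about 79% | about 90% |
| Holm, only one real (simulated, ρ = 0.5) | about 74% | about 87% |

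N = 120 assumes every Paired subject contributes, with no dropout.

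**The case against.** **The plan may not intend either result to suffice.** It never says that one significant correlation is enough. If both are required, the error rate is below 5%. This stands as a condition on the finding, but it also shows that the text leaves the criterion open.

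**The two predictors may be nearly the same measure.** If stimulation and liking were very highly correlated, the inflation would shrink: 7.0% at ρ = 0.9. The documents give no such figure.

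**A stronger reading.** A reader might infer that three primary measures are tested by four 5% tests and that the study therefore carries a 17% to 19% chance of a false claim. The arithmetic exists: 1 − 0.95⁴ = 18.5% if independent, and 17.3% to 18.3% if the Aim 1b statistics correlate 0.7 to 0.3. But the figure needs all four tests to form one family, all four nulls to be true, errors in both directions to count, and a stimulation-liking correlation below about 0.75. The documents do not support the first condition. Aims 1a and 2 are separate questions, each with its own planned test, and nothing pools the aims or makes the study positive on any one of them. Drug liking is not a primary measure, and conditioning-phase stimulation enters only as a correlate. Without liking the count is three tests and 1 − 0.95³ = 14.3%. In the hypothesised direction only, four independent tests give 1 − 0.975⁴ = 9.6%.

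Nor would four-test control be almost free. With all effects real and the plan's own sizes (80 and 40, split equally, and 90), Holm over four tests gives about 81% for Aim 1a, 92% for Aim 2 and 77% for each Aim 1b correlation, against 86%, 95% and 82% unadjusted. Declaring every other test exploratory would also demote the within-subject Aim 1a comparison, which section 3.0 states as the hypothesis and Table 2 powers.

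**Conclusion.** The concern holds for Aim 1b. One hypothesis has two unadjusted tests and no stated success criterion. If either test counts, its false-positive rate is about 8.3% to 9.5% instead of 5%. This rests on both associations being null, errors in either direction counting, and an assumed correlation of 0.3 to 0.7 between the statistics. It does not depend on how Aims 1a and 2 are treated.

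It does not extend to a finding that the study as a whole has a 17% to 19% error rate. Family-wise control across distinct mechanistic aims is a matter on which statisticians differ; the sponsor should state its choice. The effect-size analyses after every 10 subjects (section 10.0) raise a separate multiplicity question that is not counted here.

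**What to change.** Add one of the following to Aim 1b in section 9.0.

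- **Holm on the pair.** The smaller p-value is compared with 0.025 and, if it passes, the larger with 0.05. This holds the hypothesis at a two-sided 0.05 and keeps both predictors confirmatory. At r = 0.3, power per correlation falls from 82% to about 79% at N = 90 (74% if only one association is real), and from 92% to about 90% at N = 120 (87% if only one is real). At N = 90 this is slightly below the plan's 80% target.
- **One named predictor.** Make ARCI stimulation after the first methamphetamine administration the confirmatory predictor and drug liking secondary. Power for stimulation stays at 82% at N = 90; the price is that liking can no longer confirm the hypothesis by itself. The ARCI scale should be named, since section 6.0 describes two as stimulant-like (A and BG) and Table 2 uses A for Aim 2.

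Add a sentence saying whether Aims 1a, 1b and 2 are judged separately, each at 5%, or as one family. Either change is wording only, and should be made before the Aim 1b data are analysed.

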3.0 Objectives/Aims

The goal of the proposed research is to provide an understanding of how conditioned associations between methamphetamine, a prototypical stimulant drug, and distinct contexts are

formed and how the associations influence behavior, mood and responses to the drug in recreational drug users.

Aim 1a: To determine the influence of methamphetamine place conditioning upon time spent in the drug-paired context. We hypothesize that individuals will spend significantly more time in a context paired with methamphetamine at test than at the start of the experiment.

Aim 1b: To determine the relationship between individual differences in methamphetamine place conditioning and (i) acute responses to the drug, (ii) demographic characteristics. We hypothesize that individuals who exhibit greater sensitivity to the acute positive subjective effects of methamphetamine will exhibit the largest increases in time spent in the drug-paired context at test.

Aim 2: To determine context-dependent responses to methamphetamine challenge following place conditioning with methamphetamine. We hypothesize that (i) methamphetamine will produce greater subjective stimulation among subjects tested in the drug-paired room than those tested in the placebo-paired room.

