4.0 Eligibility

Healthy men and women (N=150 total) will be recruited provided they meet the screening criteria; age 18-40, body mass index 19-26kgm⁻² (previous studies in this laboratory indicate that responses to 20mg methamphetamine do not vary within this range), at least a high school education, fluency in English and a normal ECG. Exclusionary criteria are; history of a Major Axis I disorder [12], serious medical condition, history of cardiac disease, high blood pressure, history of drug or alcohol dependence (determined in the diagnostic interview), >4 alcoholic or caffeinated beverages a day, or night shift work. Subjects must report some prior recreational use of illicit drugs (incl. amphetamines) for both safety reasons (participants who report previous adverse reactions can be excluded) and data validity reasons (subjects should be able to accurately describe drug subjective effects). Subjects will be randomly assigned to 4 groups; Paired groups 1-3 (N=40 each) and an Unpaired group (N=30). The groups will be matched for prior stimulant use and sex.

Eligibility is determined during a screening process that is approved under IRB protocol 2014-1060. The criteria for the different studies that are conducted in our laboratory vary only slightly from study to study, and often subjects are screened for one study, yet qualify for another. Therefore, we find it is more cost-effective and time-efficient to conduct a general laboratory screening procedure after which subjects may be enrolled into one of a number of studies. The screening procedure is described in detail below.

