Visit 6 - Testing Session: This session will begin at 9am and is conducted at least 2 but not more than 7 days after the last drug administration session. On arrival, subjects will provide breath and urine samples to detect recent alcohol and drug use, and pregnancy in women. The session will be cancelled if any of the tests are positive. Subjects first complete a Room Preference Test (see 'Dependent Measures' section) to measure time spent in the testing rooms. Subjects will then undergo a drug challenge test in one of the testing rooms; Paired Group 1 (PG1) will receive 20mg methamphetamine in the drug-paired room, PG2 will receive 20mg methamphetamine in the placebo-paired room, and PG3 will receive placebo in the drug-paired room (NB: although we have not formulated specific hypotheses regarding PG3, this group will allow us to dissociate the contribution of expectancy and pharmacological effects to the responses exhibited by PG1). Unpaired group subjects will be randomly assigned to receive methamphetamine or placebo in one of the testing rooms. After relaxing in the designated room for 30 min, baseline measures will be collected. Subjects will then consume the capsule. Subjective measures and vital signs will be obtained every 30min (at 30, 60, 90, and 120min). At the end, subjects rate their overall experiences (see safety guidelines on page 16 for information regarding release of subjects after drug administration).

Visit 7 - Debriefing and Payment: Subjects will attend a short interview with the senior investigator one week after their final testing session at which they are fully debriefed about the study aims, the drug received and may ask questions. They are paid \$250 in cash for completing all study requirements. Subjects who drop out of the study early will be paid for the number of sessions completed based on the payment schedule below. This information is conveyed to subjects at the orientation session verbally and in the consent form.

The table below details each of the visits, the length of each visit, and the procedures that will be performed at each session during the study. The payment structure is also shown. Please note that payments are not made at each session, but are made in check form at the debriefing session as stated above.

Table 1: Study visits and procedures

Visit	Session and length	Procedures	Payment

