180 or higher	100 or higher	100 or higher	Casually ask the participant how they are feeling. If they report no other symptoms , have them sit quietly for 10min. Take another reading and if it is still in this range, contact [name] for assistance (even if they say they feel fine). If they report headache, chest pain, nausea, pounding heart or subjective distress (anxiety, tension), contact [name] for assistance right away (don't wait for a second reading).

End-of-session measurements

Vital signs must be within 20% of the baseline measurements in order to discharge the subject. If vitals are above these values, continue to monitor every 15min. Subjects who report any side effects in the medium range may require assistance to travel home (i.e., taxi cab or have a friend come to get them). If any of these conditions are present at the end of the session, do not discharge the subject until you have consulted with [name]. If all measurements are within the "normal" range (i.e., within 20% of baseline, no significant side effects), discharge the subject with a Post-session Side Effects form for them to report any unusual signs or symptoms over the next 24h.

Reporting of SAEs: Although they are unlikely, all adverse events (AEs) occurring during the course of the study will be reported to the Principal Investigator and study physician. All AEs will be followed until resolved satisfactorily. Subjects who experience AEs will be withdrawn from the study. AEs will be evaluated for SAE criteria (defined by the FDA). If an SAE should occur, it will be reported to the IRB of The University of Illinois at Chicago, NIDA, and any other appropriate agencies within 5 days of occurrence. The initial report will be followed by a complete SAE report, sent to all institutions. If a subject or the investigator discontinues the

subject's participation due to an SAE, the subject will receive follow-up medical care as necessary. Follow-up care will continue until the subject no longer requires hospitalization, the condition is stabilized with no future change expected, or the problem is determined to be unrelated to the drug used in the study. The annual progress report submitted to NIDA will contain a summary of any SAEs occurring in the previous year.

Reporting of IRB actions to NIDA: Any IRB actions on the protocol, including continuing reviews and protocol amendments, will be communicated in the annual progress report to NIDA.

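### Table 2's sample sizes (60, 80, 40) and its 70% discount do not match the planned groups; the written tests have more power than stated, so the table needs restating and enrolment does not change

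*Combined protocol and SAP*

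**What the plan says.** Section 4.0 sets the groups: "Paired groups 1-3 (N=40 each) and an Unpaired group (N=30"), so 120 paired and 30 unpaired. For Aim 1a, section 9.0 writes the between-group test as: "We will compare the change in time spent in the initially less-preferred room between the paired and unpaired groups using t-tests". No restriction to subjects who acquire conditioning is attached. For Aim 2 it compares stimulation between paired subjects challenged with methamphetamine in the drug-paired room (PG1) and in the placebo-paired room (PG2), 40 each.

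Table 2 (two-sided 0.05, 80% power for required N) has three rows:

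| Row | N | SD | Difference | Required N | Power |
|---|---|---|---|---|---|
| Aim 1a, within-subjects | 60 | 22.7 | 12.4 | 30 | 98% |
| Aim 1a, between-subjects | 80 | 20.0 | 13.7 | 70 | 85% |
| Aim 2, between-subjects | 40 | 11.0 | 13.0 | 26 | 95% |

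The footnote accounts for the Ns: "Sample sizes are lower than the number enrolled in each group as we expect 70% of subjects in the paired groups to acquire conditioning". Under Aim 1b, acquirers are subjects whose time in the drug-paired room rises by at least 10%, contrasted with "those who do not (no change or a decrease in time spent in drug-paired room"). That split is used only for exploratory comparisons. The within-subjects row matches the Aim 1a hypothesis in section 3.0, that "individuals will spend significantly more time in a context paired with methamphetamine at test than at the start of the experiment".

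**The concern.** Change in drug-paired room time is the first primary measure. Table 2 does not tell the reader how many subjects per group enter its comparison, or whether non-acquirers count. The N of 80 has no stated split, and the reason given for it does not lead to it.

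The discount also conflicts with the written analysis. Acquisition is read off the change in room time, which is the Aim 1a outcome. Someone who took the footnote as an analysis rule and kept only acquirers would select the paired arm on the endpoint and compare it with an unselected unpaired arm. That would bias the comparison in favour of conditioning.

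**Working it through.** **Inputs.** Group sizes are from section 4.0; differences, SDs, alpha and target power are from Table 2. Losses of 10% and 20% are assumptions: the plan foresees dropouts ("Subjects who drop out of the study early will be paid for the number of sessions completed") and withdrawals ("Subjects who experience AEs will be withdrawn from the study") but gives no rate.

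**Method.** Two-sample t-test, noncentral t, with λ = difference / (SD × √(1/n₁ + 1/n₂)) and n₁ + n₂ − 2 degrees of freedom.

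**1. Reproducing Table 2.**
- Aim 1a between-subjects: 13.7/20.0 = 0.685. At 40 vs 40, λ = 0.685/√(1/40 + 1/40) = 3.06 and power is 85.7% (stated 85%). At 35 + 35 = 70 power is 80.6%, and at 34 + 34 it is 79.5%, so the required N of 70 is an equal-group figure.
- Aim 1a within-subjects: 12.4/22.7 = 0.546. Power is 98.6% at 60 (stated 98%), and 80% power needs 29 (stated 30).
- Aim 2: 13.0/11.0 = 1.182. Power is 95.4% at 20 vs 20 (stated 95%), and 13 + 13 = 26 meets 80%.

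The arithmetic is sound for those group sizes. The question is whether they are the trial's.

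**2. Applying the footnote's discount to the planned groups.**

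| Row | 70% of planned paired subjects | Table N |
|---|---|---|
| Within-subjects | 0.7 × 120 = 84 | 60 |
| Paired vs unpaired | 84 + 30 = 114 | 80 |
| PG1 vs PG2 | 0.7 × 80 = 56 | 40 |

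None agrees.

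**3. Aim 1a with 30 unpaired subjects.** A 40 vs 40 split is not available. With 30 unpaired, 50 + 30 = 80 gives 83.4%, 40 + 30 = 70 gives 79.8%, and 41 + 30 = 71 gives 80.3%.

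**4. The tests as written.** For Aim 1a at 120 vs 30, λ = 0.685/√(1/120 + 1/30) = 0.685/0.2041 = 3.36.

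| Paired vs unpaired | Power at 13.7/20.0 | Difference detectable with 80% power |
|---|---|---|
| 120 vs 30 (full completion) | 91.5% | 11.5 points |
| 108 vs 27 (assumed 10% loss) | 88.5% | 12.1 points |
| 96 vs 24 (assumed 20% loss) | 84.5% | 12.9 points |

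Aim 2 gives 99.9% at 40 vs 40 and 99.6% at 32 vs 32 (assumed 20% loss). The within-subjects test at 120 exceeds 99.9%.

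**5. Conditional check on the pilot source.** Suppose that 13.7/20.0 came from acquirers only, and that non-acquirers change no more than the unpaired group. Both are assumptions. The all-paired difference is then 0.7 × 13.7 = 9.59. At 120 vs 30 power is 64.6% with SD 20.0. With the SD enlarged for the mixture, √(20.0² + 0.7 × 0.3 × 13.7²) = 20.96, it is 60.5%.

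**The case against.** The strongest reply is that nothing in the trial turns on this. Power for the written tests exceeds the stated values, and the Ns may be deliberate caution. The first part stands and keeps the point minor. The second does not rescue the table, because the caution offered as its reason does not produce its numbers.

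It can also be said that 85% is close to what 30 unpaired subjects deliver: 50 + 30 gives 83.4%. That is true, and the fault is not a large numerical error. The table gives no split, and neither 50 + 30 nor 40 + 40 is the planned comparison.

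A further reply is that the analysis set is for the sponsor to choose. The written tests already include everyone, so the proposal only states what they say. For Aim 2, the preference test precedes the challenge at Visit 6, so restricting to acquirers would not select on that aim's own outcome. If it is intended, it must be written down.

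Three inferences go further than the documents allow:
- A reader might infer that the required 70 is wrong and that about 107–110 subjects are needed. That holds only if the unpaired group shrinks with the paired at a fixed 4:1, which no section proposes. With unpaired held at 30, a total of 70 gives 79.8%, practically the 80% target.
- A reader might infer that the table survives from paired groups of 30, since 3 × 30 matches the N of 90 in Aim 1b and 70% of 30 is 21. This is plausible for 60 and 40, but it leaves 80 unexplained and the documents do not say so.
- A reader might take the within-subjects row as evidence that the pilot subjects were unselected, because a normal distribution with mean 12.4 and SD 22.7 puts 29% at or below zero, near the plan's 30% non-acquirers. The same model puts only 54% at or above the 10-point threshold, against 70% acquirers, so it settles nothing.

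**Conclusion.** The point holds as a minor reporting fault. Table 2's Ns follow neither from 120 paired and 30 unpaired subjects nor from the 70% discount, and that discount should not set the N of an Aim 1a test run on unselected groups. The stated 85% and 95% are not the power of the written tests, which is 91.5% and 99.9% at full completion. Aim 1a stays at 84.5% under an assumed 20% loss.

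These figures rest on the table's own differences and SDs and on those coming from unselected pilot subjects. The pilot section and figure that Table 2 cites are not available here, so this cannot be confirmed. A reader might infer that the trial is underpowered; the documents do not support that. The 61–65% figure applies only if both assumptions of the conditional check are true, and neither is stated in the plan.

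**What to change.** In section 9.0 and Table 2:

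1. Remove the 70% discount from the Ns and delete the footnote's explanation.
2. State that Aim 1a compares all paired with all unpaired subjects, and Aim 2 all of PG1 with all of PG2, regardless of acquisition.
3. Show n per group: 120 vs 30 for Aim 1a, 40 vs 40 for Aim 2, and 120 for the within-subjects row if that test is kept.
4. Give power at full completion and at a stated assumed loss. For Aim 1a add the difference detectable with 80% power: 11.5 points, or 12.1 to 12.9 with 10–20% loss.
5. If a required N is kept, state its allocation: about 41 paired with 30 unpaired, or about 107–110 in total only if 4:1 is held.
6. Say which pilot subjects gave 13.7/20.0. If they were acquirers only, report the lower power (about 61–65% if non-acquirers match the unpaired group).

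The cost is a few sentences, a revised table and one check of the pilot data. No subjects or visits are added.
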